### **SECTION I: RESEARCH PLAN**

1. **Statement of Purpose:** State the scientific aim(s) of the study, or the hypotheses to be tested.

**PRIMARY AIM 1.** To conduct a double-blind, placebo-controlled parallel group study to evaluate the efficacy of naltrexone HCI and bupropion HCI (NB) versus placebo in patients with binge-eating disorder (BED), stratified by obesity status (n=50 per cell, n=200 total).

- *Hypothesis 1.1.* We hypothesize that NB will be superior to placebo for reducing binge eating among patients with BED.
- Hypothesis 1.2. We hypothesize that NB will be superior to placebo for reducing weight among BED patients with obesity.
- Hypothesis 1.3. We will examine whether BED patients with and without obesity derive differential benefit of NB versus placebo on reducing binge eating (i.e., does obesity moderate outcomes).

**PRIMARY AIM 2.** To evaluate correlates and possible mechanisms underlying the effect of NB on binge eating among all participants (n=50 per cell, N=200 total). To evaluate the effect of NB on hypothalamic melanocortin and brain reward systems, eating behavior will be assessed with an established human laboratory paradigm designed to evaluate the ability to resist eating preferred high-caloric food and subsequent over-eating. We will evaluate potential mechanisms including eating peptides (leptin, ghrelin) involved in both homeostatic and hedonic aspects of eating, as well as food craving, mood, hunger, and control over eating.

Hypothesis 2.1. We hypothesize that potential medication-related changes in eating behavior, eating peptides and craving assessed in the laboratory will mediate clinical outcomes during the 12-week treatment period (i.e., rates of binge eating).

Hypothesis 2.2. We hypothesize that NB versus placebo will increase the ability to resist eating preferred high-calorie food, and will reduce overall calorie consumption in patients with BED.

Hypothesis 2.3. We will examine whether BED patients with and without obesity derive differential benefit of NB versus placebo with regards to their ability to resist eating or calories consumed (i.e., does obesity moderate outcomes).

**EXPLORATORY AIM 3**. To assess eating and drinking behavior, food craving, and mood 'in the field' in a subset of participants (n=60).

2. **Probable Duration of Project:** State the expected duration of the project, including all follow-up and data analysis activities.

September 2017 – September 2024

3. **Background:** Describe the background information that led to the plan for this project. Provide references to support the expectation of obtaining useful scientific data.

Binge-eating disorder (BED) is a prevalent, refractory, and serious health problem, with national estimates identifying that 2.6% of adults meet criteria for BED [1]. With the recent inclusion of BED as a formal DSM-5 diagnosis [2], there has been increased attention on identifying effective pharmacotherapies for this disorder. This application focuses on evaluating the therapeutic potential of naltrexone combined with bupropion for BED.

Recognized as a serious problem by Stunkard [3], only recently has BED become a research focus and established as a formal diagnosis in the DSM-5 [2]. BED is defined by recurrent episodes of binge eating without compensatory weight control methods that characterize bulimia nervosa. Binge eating is defined as eating an unusually large amount of food given the context coupled with a subjective sense of loss of control and diagnosis requires binge eating to be associated with marked distress [4]. Epidemiologic studies have found that BED is more prevalent than the other two formal eating disorders [5]. Estimates of BED are higher in adults with obesity (8%) and are much higher in most clinical settings [6, 7]. Of adults with current BED diagnosis, 42% meet criteria for obesity (BMI > 30) whereas 58% do not meet criteria for obesity (BMI < 30) [8]. BED is strongly associated with obesity, with rates of BED disproportionately increasing with increasing BMI. Adults with BED are 4 to 10 times more likely to present with BMI's of 30 or 40 or more, respectively [8]. BED may be a contributor to the development of obesity [9] and associated metabolic problems [10] in vulnerable individuals.

Compared to other eating disorders, BED is prevalent across gender and ethnic/racial groups [11]. The prevalence of BED in the National Co-morbidity Survey Replication [1] was 3.5% among women and 2.0% among men. BED has diagnostic validity [12], is a stable construct [13], differs from other eating disorders and obesity [14-16], is strongly associated with elevated risk for psychiatric, and psychosocial problems [5, 15, 17, 18]. BED is associated with substantially increased risk of several chronic health conditions including cardiometabolic disorders, musculoskeletal disorders, pain, and ulcers [8, 19], even when adjusting for BMI [10].

Overall, several medications have short-term efficacy relative to placebo [20] and certain psychological treatments have efficacy [21] with important advantages over medication (alone or in combination) [20].

Pharmacotherapy for BED has received research attention, albeit nearly all RCTs have been of short duration and without follow-up period to establish durability [20, 22, 23]. Critical review and meta-analysis show that

several drugs – working through varied mechanisms – have short-term efficacy relative to placebo for reducing binge eating and produce weight loss ranging from modest to none [20]. Placebo-controlled trials of anticonvulsants topiramate and zonisamide [24-26] have reported effects for reducing both binge-eating and weight (average weight loss of roughly 3-4 kg compared to placebo), but have also shown high dropout and frequent adverse events that become near-universal and troubling with longer use [27]. SSRI antidepressants, initially regarded as a potential treatment strategy [e.g., 28] are characterized by small effect sizes relative to placebo [20], produce no weight loss at all [29] and are inferior to CBT [29, 30].

Lisdexamfetamine dimesylate (LDX) for BED. An important development was the FDA approval in January 2015 of a CNS stimulant, LDX, for the treatment of moderate-to-severe BED. Approval was based on findings from an integrated series of studies funded by the manufacturer. The phase II RCT demonstrated that 50mg and 70mg were superior to placebo [31, 32] for reducing binge-eating days and reported binge-eating abstinence rates of LDX versus placebo (Study 1: 40% versus 14%; Study 2: 36% versus 13%) at the end of the 11-week treatments. Importantly, no longer-term follow-up are presently available.

We are not using LDX for several reasons. The binge remission outcomes for LDX at 11-weeks [31] are less robust than those reliably produced by BWL for BED, and BWL outcomes are durable through 12-months post-treatment [33]. Most importantly, although LDX was associated with weight loss (mean 4.9 kg) [32], weight loss was examined as a safety measure, not a clinical outcome. The FDA approval and manufacturer product labeling included a Limitation of Use highlighting that LDX is not indicated or recommended for weight loss. This is because other CNS-stimulant sympathomimetic medications for weight loss have been associated with severe cardiovascular problems and the safety and efficacy of LDX for obesity have not been demonstrated.

Pharmacotherapy for Obesity. Sibutramine, which was effective for reducing both binge eating and weight in BED [34, 35], was withdrawn from the market in 2010 due to cardiovascular concerns. This left orlistat as the sole FDA-approved anti-obesity medication for longer-term use [36], until 2012. Placebo-controlled trials of orlistat for BED [37, 38] reported significant yet very modest effects for weight loss, but not for reducing binge eating when added to BWL or CBT. A recent RCT testing orlistat combined with BWL reported a moderator effect of significantly greater weight loss for orlistat than placebo for obesity without BED, but not for obesity with BED [39].

The 2012 FDA approval of two new anti-obesity medications (phentermine/ topiramate and lorcaserin) [40, 41] came after heated debate given significant concerns about limited efficacy and safety profiles, and questions about serious medical complications with longer use [40, 41]. The low rates of achieving 5% weight loss (less than 30% in all three of the phase III RCTs) was inflated due to the use of completer analyses despite the observed high drop-out rates (e.g., 45% in the BLOOM Trial) [42]. The combination phentermine/ topiramate had the highest effect sizes for weight loss, but this needs to be considered against the unfavorable adverse event and tolerability profile.

Behavioral Treatment for Obesity. Behavioral Weight Loss (BWL) counseling has been evaluated among patients with comorbid BED and obesity. BWL, a widely available "generalist" intervention, achieves good binge-eating outcomes plus produces modest weight loss over the short-term in persons with BED who also have comorbid obesity [43, 44]. BWL for BED in persons with co-morbid obesity outcomes, however, are less durable over time [44] and the observed weight losses achieved with BWL for BED appear to be dampened relative to those generally reported for BWL for obesity without BED [45, 46]. These results highlight that behavioral treatments for patients with BED and comorbid obesity do not produce consistent effects on both binge eating and weight loss, identifying a need for further treatment development. Additionally, many

people with BED do not have excess weight or obesity and BWL for "normal weight" persons with BED has not been tested.

A test of NB for patients with BED without obesity is needed and the mechanistic background for NB medication supports the rationale for use in BED. The current RCT will test pharmacological treatment (without any behavioral intervention) so that findings are more scalable and broadly translatable to generalist settings. The published RCT pharmacotherapy literature for BED consists mainly of med-only vs placebo-only trials ranging from 6 to 24 weeks (many are 12 weeks) [23].

We performed a pilot RCT (HIC# 1409014705) with N=22 patients with BED and obesity and delivered the NB pharmacotherapy without concurrent behavioral weight loss. We observed no problems in the conduct of the pilot RCT. The pilot RCT found that NB was well-tolerated, reduced the frequency of binge eating, and promoted weight loss in the obese patients with BED with moderate effect sizes. Finally, we have an on-going recently-funded RCT (HIC# 1506016065) that is examining intensive BWL and NB, alone and combined (i.e., balanced 2 x 2 factorial design; thus, some patients also receive NB without BWL) in patients specifically with BED with obesity.

### NB Pharmacotherapy

In September 2014, the FDA approved the combination of naltrexone and bupropion to treat obesity consisting of the following empirical support from several RCTs performed with obesity (but not BED). The putative mechanisms of action are described in Section VI.

Obesity Outcomes. Several large RCTs have reported that NB was effective in promoting significant, clinically-meaningful weight loss in patients with obesity [47-49]. NB showed greater weight loss than placebo, -6.5 vs -1.2% [49]; -8.2% vs -2.1% [48], and the following percentages achieving 5% weight loss: 56% vs. 18% [48], 52% vs. 15% [49]. Apovian, Aronne [50], in a study of 1496 patients with obesity, reported greater weight losses relative to placebo (-6.5% vs -1.9% at week 28 and -6.4% vs -1.2% at week 56) and greater likelihood of achieving 5% weight loss (56% vs 18% at 28 weeks).

The putative mechanisms of action for the two medications are relevant for binge eating in addition to weight loss. Naltrexone, an opioid receptor antagonist, is approved for treatment of alcohol and opioid dependence (O'Malley, Sinha, [name], et al., 2007). Naltrexone produces weight loss in lab animals but only minimal weight losses in most human studies (Malcolm et al. 1985; Billes & Greenway, 2013). Bupropion is thought to operate through dopaminergic, noradrenergic, and nicotinic acetyl-cholinergic mechanisms [51-53], may target reward processes that drive eating behaviors, consistent with its FDA indication for treating nicotine dependence and reduced weight gain during smoking cessation [54, 55]. Bupropion has been found to promote weight loss in several obesity RCTs. Li and colleagues [56], in a meta-analysis of five trials of bupropion, reported a mean difference in weight loss of 2.77 kg (Cl, 1.1 to 4.5) between bupropion and placebo groups at 6 months. White & [name] (2013) first reported preliminary support for a possible (albeit modest) weight loss benefit specifically in obese BED patients (see C.1).

4. **Research Plan:** Summarize the study design and research procedures using non-technical language that can be readily understood by someone outside the discipline. **Be sure to distinguish between standard of care vs.** research procedures when applicable, and include any flowcharts of visits specifying their individual times and lengths. Describe the setting in which the research will take place.

Overview of Study Design

This single-site, proof-of-concept, clinical trial is a double-blind, placebo-controlled, parallel group study to test the effectiveness of naltrexone + bupropion (NB) pharmacotherapy in BED patients with and without obesity. BED patients with (BMI > 30 and <50) and without obesity (BMI >21.5 and <29.9), will be randomized to NB (32 mg/day naltrexone combined with 360 mg/day bupropion) or placebo (n=50 per cell, n=200 total).

Following eligibility screening and randomization, participants will start a 12-week medication treatment period, a treatment period consistent with other BED medication trials (McElroy et al., 2016). Participants will have four weeks of up-titration: one tablet daily (Naltrexone 8mg/ Bupropion 90mg; 1 week), then two tablets daily (Naltrexone 16mg/ Bupropion 180mg; 1 week), then three tablets daily (Naltrexone 24mg/ Bupropion 270mg; 1 week), to reach the full dose of four tablets daily (Naltrexone 32mg/ Bupropion 360mg). The dosage will continue for the remainder of the 3 months. Medication will be discontinued at the end of 3 months, and patients will then be followed 12-months post-treatment to assess the durability of medication effects. The primary outcome measure is reduction in binge-eating frequency.

To evaluate correlates and mechanisms of NB on eating behavior, assessments will occur in the laboratory and in the field to optimize internal and external validity. Participants will complete human laboratory sessions ("lab sessions") before the start of medication and then during the final week of the 12-week medication period to evaluate the ability to resist eating preferred high-caloric food and subsequent overeating. During the laboratory sessions, we will evaluate potential mechanisms including eating peptides

(leptin, ghrelin) involved in both homeostatic and hedonic aspects of eating, as well as food craving, mood, hunger, and control over eating. Participants who are unable to complete a baseline lab session prior to the start of treatment may complete the lab session 4-6 weeks after beginning treatment. We believe that this period of time is sufficient to capture medication effects on eating behavior.

Finally, we plan to monitor ambulatory dynamic changes in stress with a wearable biosensor and collect daily information regarding eating behavior with self-initiated, scheduled, and random prompts to a smartphone 'in the field' during the first 6 weeks of the 12-week treatment period in a subset of participants (n=15 per cell, n=60 total; "Biosensor"). Eating and drinking behaviors will be tracked using an Android smartphone that is synced with a smartwatch (Garmin Vivosmart 4) to passively track stress states. During real-time episodes of calorie consumption, participants will be prompted to answer questions delivered to their smartphone related to food craving, mood, and stress.

[figure not shown]

Figure 1. Overview of Study Design

**Pre-Screening**: Participants responding to recruitment efforts will be screened by telephone. If participants prefer to answer some of the pre-screening questions through the Yale Qualtrics system, participants will indicate their consent to the recruitment/pre-screening process in the online system. After the initial telephone screening, potentially eligible participants will be scheduled for an in-person assessment; participants will complete survey measures of eating behaviors and psychopathology and psychosocial functioning around the time of the in-person appointment. Potential participants will meet with a research assistant who will obtain informed consent and will screen the participant for inclusion and exclusion criteria. Participants who provide informed consent and are determined to be eligible will then participate in the study as depicted and described in the following paragraphs. See also Figure 1.

**Baseline Assessment**: Participants will complete a physical exam, vitals, and routine laboratory blood work (including lipid profile, Hb1Ac, and liver function tests) at which time the study physician will review the subject's medical status and medical eligibility criteria. Patients will also have a urine screen for opiates. As part of the determination of eligibility, participants will complete two interviews, the MINI International Neuropsychiatric Interview-Version 7.0 (MINI) and Eating Disorder Examination (EDE) to generate psychiatric

diagnoses and detailed current eating disorder features and diagnoses. Other measures, for safety and establishment of baseline values, will also be obtained: BMI, vitals, eating behaviors, mood, and quality of life.

For a full description of instruments, see "Measures," which includes a grid depicting when each measure is administered. The baseline assessment will occur over 1-2 in-person meetings and is estimated to take a total of 2-3 hours in-person.

Randomization. Eligible participants who agree to participate and provide written informed consent will be randomized in equal proportions to one of the two treatments (using blocked randomization with random block sizes of 4 and 8 to obviate any secular trends). Gender will be balanced across cells (60% female). We will monitor randomization procedure and determine whether any systematic differences in demography (age, ethnicity/race) or clinical characteristics (psychiatric co-morbidity) become evident. We will consider adjustment to randomization if indicated (Kraemer & Fendt, 1990; Kraemer & Pruyn, 1990). The Biostatistician, [name], will be responsible for developing the randomization schedule in conjunction with the Investigational Drug Pharmacy (IDS), at Yale-New Haven Hospital. The IDS will randomize participants to medication groups. Research study staff (clinicians and outcomes assessors) and participants will all remain blind to the medication condition.

Treatment Protocol for Naltrexone/Bupropion (NB) Pharmacotherapy. Medication will be prescribed at recommended doses per FDA-approval for obesity. NB medication will comprise naltrexone sustained-release (SR, 32 mg/day) combined with bupropion SR (360 mg/day) taken daily (8 mg naltrexone/90 mg bupropion in each tablet/capsule, two of which will be taken twice daily; both conditions will have the same frequency). Following regimens in previous RCTs, a dosing escalation approach will be used, beginning with a quarter of the full dose and increasing it weekly until the full dosing is achieved at week 4 (Greenway et al., 2010; Wadden et al., 2011). This dosing will continue for the remainder of the trial unless the patient develops intolerable side effects. If such occur, the physician may reduce the dosing to achieve tolerability. If the patient cannot tolerate the medication, has adverse effects, or is non-compliant with medication for > 7 consecutive days, s/he will be discontinued from the medication arm. For all participants taking medication for greater than 4 weeks, a 7-day taper will be provided. Physician/medication-management visits will be brief (10 minutes) and will focus on compliance with dosing and evaluating side effects. These visits will occur twice during first month and monthly thereafter unless clinical concerns require additional contacts. At the onemonth treatment visit and at the end of treatment, patients will have their blood drawn to measure hepatic function for safety. Blood draws will occur either at Quest Diagnostics, at the Hospital Research Unit, or at the Church Street Research Unit. After the 12-month follow-up, patients will be informed (by research pharmacist) whether they were on NB or placebo. Medication double-blind will be maintained for the investigators and assessors until all participants have completed final 12-month follow-up assessments.

Monitoring and enhancing medication compliance. In addition to physician visits, several procedures will be used to monitor and enhance medication compliance including drug packaging, reminder calls, pill counts, and plasma trough medication levels. As we have done in prior studies, medication compliance will be assessed with pill counts. Medication will be dispensed in pill bottles; adverse events will be assessed at each appointment. Medication compliance will also be monitored through evaluation of a plasma level of naltrexone, 6-beta-naltrexol, and bupropion at weeks 4 and 12. Importantly, we plan to explore the relationship between compliance and study outcomes.

Withdrawal from Treatment and Other Treatments. Withdrawal/attrition from treatments will be examined. Use of other treatments during study will be assessed and considered in analyses. Patients will be asked about all forms of treatments during major assessments. We have considered criteria for removal of patients

from the study, including worsening depression, suicidal ideation or binge eating, or failure to comply with medication. Previous experience suggests that worsening clinical status is rare; in such cases, [name] and study physician would determine whether to remove the person from the study and provide referrals.

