### Procedures for Modeling Cue-Induced Eating Behavior.

Each participant will complete two laboratory sessions, the first scheduled prior to starting medication, and the second at the end of medication treatment (week 11-14). This pre-post evaluation by medication group will provide a powerful test of medication effects. Alternatively, if the pre-treatment laboratory session cannot be schedule prior to the beginning of treatment, participants may complete the session around one month of treatment (week 4-6). If we are unable to reschedule at the HRU/CSRU, the lab session will take place at [name] in dedicated lab rooms in [name] research space. Our previous eating study (HIC# 0909005678, [name]) took place in this setting and was very successful. There will be no blood collected throughout the lab session if it occurs at [name], but baseline samples will be obtained on the 4th Floor YCCI unit. All other lab procedures will remain the same. Participants will not be excluded from the treatment study if they are not willing to do the lab sessions, or if they are not able to be scheduled for the lab sessions. Research procedures related to the treatment study (e.g., blood draws for liver function, lipids, and metabolic function) will still be drawn if lab sessions are not completed.

Laboratory sessions will be completed at the Hospital Research Unit (HRU) of the Yale Center for Clinical Investigation (YCCI) located at Yale-New Haven Hospital or the Church Street Research Unit (CSRU) at [name]. Participants will be instructed not to eat past 10:00pm the night before the laboratory session. They will arrive at the HRU/CSRU at 7:30am. At the start of the lab session, participants will have an IV cannula inserted and complete the baseline assessments listed in **Table 1**. Participants will then receive breakfast to standardize time since last food consumption. Breakfast will be a breakfast bar that is approximately 150 calories provided by the Research Team. Participants will then be food deprived for the next 3 hours. Based on our prior work, this length of food deprivation is sufficient to increase food craving. After 3 hours of food deprivation, participants are presented with preferred high-caloric snacks. Participants will be asked to take their study medication prior to the second lab session. Scheduling is limited to HRU/CSRU and participant availability.

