The system involves a smartwatch that participants will wear on their non-dominant hand. The system is linked to a smartphone. Participants will be provided with a phone to use for the study duration. Participants will wear the system for the first six weeks of the 12-week medication period (3 weeks medication titration + 3 weeks at full dosing). We believe that this period of time is sufficient to capture medication effects on eating behavior. These "real-time" consumption behavior data, along with associated proximal data regarding behavior, mood, and stress variables — will be analyzed within subjects over time (to understand dynamic

time-varying factors) and between subjects and these data will be linked to the available treatment outcome data including follow-ups.

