### Safety and Compliance

- Blood Pressure (**BP**) and Heart Rate (**HR**). BP readings (both systolic and diastolic) and HR will be obtained regularly at assessment meetings.
- Systematic Assessment for Treatment Emergent Effects (**SAFTEE**) [90] Adverse events will be assessed in person during study related appointments.
- Columbia Suicide Severity Rating Scale (**C-SSRS**) [91] is a semi-structured assessment intended for administration by clinicians or study staff during scheduled study visits. It explores suicidal ideation and intensity, as well as behaviors and lethality.
- Pill Counts. Participants will be asked to bring their medication to their last appointment and clinicians will count and record the number of pills remaining.
- Naltrexone and Bupropion levels plasma will be collected at weeks 4 and 12 to evaluate plasma trough levels of bupropion, naltrexone, 6-beta-naltrexol levels.

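### A first lab session done on medication at weeks 4-6 has no time level of its own; left in the baseline slot, it dilutes the contrast that opens the Aim 2 mediation analysis

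*Combined protocol and SAP*

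**What the plan says.** **Lab sessions.** Section I, item 4 (Overview of Study Design) places the two lab sessions before medication and in the last week of the 12-week course. It then allows a missed first session to be replaced by a "lab session 4-6 weeks after beginning treatment. We believe that this period of time is sufficient to capture medication effects on eating behavior". Procedures for Modeling Cue-Induced Eating Behavior repeats the permission and relies on the two-session layout: "This pre-post evaluation by medication group will provide a powerful test of medication effects". The assessment grid (Figure 2) has LAB #1, in the pre-treatment block, and LAB #2, and no other lab column.

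**Dose at weeks 4-6.** The treatment protocol speaks of "increasing it weekly until the full dosing is achieved at week 4", the Overview says "Participants will have four weeks of up-titration", and the biosensor procedures count "3 weeks medication titration + 3 weeks at full dosing". These passages should be reconciled. On any of them the participant is on study medication at weeks 4-6, usually at or near full dose, although dose reduction is allowed.

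**Analysis.** Section I, item 13 specifies mixed models with time as a within-subject factor, first treated as categorical, and refers to time points specific to each aim. The Primary Aim 2 paragraph names none for a late first session. It takes a lab variable forward to mediation only after a significant time-by-medication effect, and it also counts a significant drug main effect on the lab variables as support.

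**Lab 2.** The Overview puts it in the final week of 12 and stops medication at 3 months. The lab procedures allow weeks 11-14 with study medication taken beforehand. Two other sections provide a 7-day taper.

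**The concern.** By the protocol's own account, a week 4-6 session can already show the drug effect, so it is not a baseline. Yet the only slot open to it is the baseline slot. If it is analysed there, the active arm's baseline already contains part of the effect, and the change from session 1 to session 2 understates that effect.

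That change is the gate for Hypothesis 2.1: a lab variable that fails it is never tested as a mediator. If mediation uses change in the lab variable, the same sessions also distort the mediator. And with no coding rule in the plan, the choice could be made after the data are seen.

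**Working it through.** **Inputs from the documents.** 200 participants randomised equally, so at most 100 per arm (lab sessions are optional); two-sided alpha 0.05, the level stated for primary outcomes; two lab time points. The documents give no Aim 2 effect size, SD, power, displaced share or between-session correlation, so there is no stated figure to reproduce.

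**Assumptions.** Lab 2 effect d = 0.40 SD, outcome SD 1, correlation r = 0.5, n = 100 per arm, f = 10% or 20%, g = 0.25 to 1, displacement unrelated to arm.

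**A. Late session left as baseline.** The active arm's baseline mean shifts by fgd, so the contrast is d − fgd = d(1 − fg). SE = √(4(1 − r)/n) = √(2/100) = 0.1414. (The small extra variance from mixing sessions is ignored.)

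**B. Late session given its own level; 1-df contrast of lab 2 with true baseline.** The contrast is d. SE = √(2[(1 − r)²/n + (1 − r²)/((1 − f)n)]). At f = 10%: √(2[0.0025 + 0.75/90]) = 0.1472. At f = 20%: √(2[0.0025 + 0.75/80]) = 0.1541.

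**B2. As B, but with the gate left as the omnibus interaction.** Three time levels give 2 df. The noncentrality is 7.46 at f = 10%, g = 0.5 and 6.83 at f = 20%, g = 1.

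**C. Drug-placebo difference at lab 2, pre-medication means constrained equal.** 1/SE² = n(1 − f)/(2(1 − r²)) + nf/2. At f = 0: 100/1.5 = 66.7, SE 0.1225. At f = 10%: 60 + 5 = 65, SE 0.1240. At f = 20%: 53.3 + 10 = 63.3, SE 0.1257.

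| f, g | A: contrast | A: power | B | B2 | C |
|---|---|---|---|---|---|
| 0 | 0.40 | 80.7% | 80.7% | n/a | 90.4% |
| 10%, 0.25 | 0.39 | 78.7% | 77.6% | 69.8% | 89.7% |
| 10%, 0.5 | 0.38 | 76.6% | 77.6% | 68.5% | 89.7% |
| 10%, 1 | 0.36 | 72.1% | 77.6% | 68.4% | 89.7% |
| 20%, 0.25 | 0.38 | 76.6% | 73.7% | 67.7% | 88.9% |
| 20%, 0.5 | 0.36 | 72.1% | 73.7% | 64.9% | 88.9% |
| 20%, 1 | 0.32 | 61.9% | 73.7% | 64.4% | 88.9% |

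Simulation (20,000 runs) agrees for A: 0.380 and 76.5% at f = 10%, g = 0.5; 0.321 and 61.7% at f = 20%, g = 1.

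**Fewer lab completers.** The attrition range that the monitoring plan cites from earlier studies (20% to 38%) would leave 80 or 62 per arm. At f = 20%, g = 1, power under A, B and C is then 52.6%, 64.1% and 81.3%, or 42.9%, 53.3% and 70.8%.

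**Reading the table.** A is biased whenever fg > 0. B removes the bias but discards baselines, so it beats A only when g is large enough; at g = 0.25 it has less power than A. B2 is below A everywhere except f = 20%, g = 1. The gain under C is mostly the model's: it is already 90.4% against 80.7% with nobody displaced.

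**The case against.** **The plan never says that a late session will be analysed as baseline.** This stands. The mixed model accepts unequal numbers of observations and categorical time, and the protocol's remark about medication effects could mean that the session is an on-treatment measure. A reader might infer that the plan commits to a biased analysis. What the documents show is a session allowed on medication, two slots to hold it, and no rule. The dilution is conditional on baseline coding.

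**The size is unknown.** This also stands. The biosensor procedures use the same sentence about capturing medication effects for their six-week monitoring period, so it says little about g in the lab. If late sessions, being closer in time, correlated 0.7 with lab 2, baseline coding would have slightly more power than B at g = 0.5 (78.3% against 77.6% at f = 10%; 75.6% against 73.7% at f = 20%), though still a biased contrast.

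**Recoding might be thought to restore power by itself.** It does not, as B and B2 show. A third time level with the gate left as an overall interaction can cost more power than the dilution does.

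**Two further inferences go beyond the text.** The main effect in the Aim 2 paragraph could be read as an average over both sessions, which would halve the effect to 0.20 SD and give 37.2% power with nobody displaced. It may instead mean regardless of obesity status, as the Aim 1 paragraph says explicitly; the wording should settle this. Nor does the Aim 2 paragraph define a mediator change score. It speaks of improvement and describes regressions, so an effect of late sessions on the mediator depends on how improvement is computed.

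**Conclusion.** The concern holds in a limited form. The protocol permits an on-medication first session, provides no time level for it, and makes mediation depend on the contrast that such sessions would dilute. If they are kept in the baseline slot, the contrast shrinks by the factor (1 − fg). The direction follows for any positive f and g if displacement is unrelated to arm; under that condition the bias can close the gate but cannot open it falsely.

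The power loss runs from 2.0 points (80.7% to 78.7%) to 18.8 points (80.7% to 61.9%) over the range shown. A large loss needs f near 20% and g near 1, and the documents support neither value. A reader might also infer that the main efficacy result is at risk. It is not: Aim 1 does not use the lab sessions, and the between-arm difference at lab 2 does not depend on when the first session took place. This should be fixed, but it does not threaten the trial's primary efficacy conclusion.

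**What to change.** 1. Code each lab session by its date relative to the start of medication. Never enter a week 4-6 session as baseline; give it its own on-treatment level, and report the number of such sessions per arm.
2. Name one single-df contrast as the Aim 2 test and the mediation gate: the drug-placebo difference at lab 2, from a longitudinal model with pre-medication means constrained equal across arms. It should replace both the overall time-by-medication test and any main effect averaged over sessions. Participants without a true baseline still contribute their lab 2 data.
3. If mediation uses change in a lab variable, take the baseline only from true pre-medication sessions.
4. Reconcile the two statements of lab 2 timing with the passages on stopping and tapering medication. As written, a session in week 13 or 14 could fall during or after the taper. Keep all lab 2 sessions in the intent-to-treat contrast.

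The cost is SAP wording, one time code taken from a date already recorded, and slightly more analysis work; no new measurement is needed. The gate is redefined, which should be done before unblinding. Mediation based on change has fewer baselines (at most 180 or 160 of 200 at 10% or 20% displaced), and precision falls slightly (power 90.4% to 88.9% at 20% displaced).
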